12 STATISTICAL CONSIDERATIONS

Statistical analysis of this study will be the responsibility of the Biostatistics and Data Management Core at the Indiana University Melvin and Bren Simon Cancer Center (IUSCC). Parameter estimates and relevant summary statistics will be reported where appropriate. For continuous variables, summary statistics will include number of subjects, mean, median, standard deviation, minimum and maximum. Categorical endpoints will be summarized using number of subjects, frequency, and percentages. Missing data will not be imputed. Data analysis will be performed in SAS Version 9.4. Additional exploratory analyses of the data will be conducted as deemed appropriate. Changes from this analysis plan will not require an amendment to the protocol unless it changes a significant feature of the protocol.

The statistical analysis methods are outline below.

12.1 Study design

A Pilot, Phase 2, Non-randomized, Single Institution Study

12.2 Study population

The enrolled population comprises all patients who meet the eligibility criteria and are registered onto the study and who are treated on this protocol.

12.3 Sample size

The study consists of a total of 20 patients divided equally between two treatment arms that will be studied simultaneously:

- Arm 1: 10- partial nephrectomy for localized RCC (no lymph nodes)
- Arm 2: 10- radical nephrectomy and lymph node dissection for locally advance or metastatic RCC.

A total sample size of 20 was determined to balance the competing goals of assessing the primary and secondary while not exposing more patients to an investigational procedure than is required. Also, there is an 88% probability of seeing at least one toxicity event if the probability of that toxicity is 0.10. Thus, we feel confident that with a sample of size 20, we will be able to detect unacceptable toxicities that have probabilities of 0.10 or higher.

A sample size of 10 for each arm was chosen. If we do not observe sensitivity for detection of RCC of at least 70% in each arm, we will consider further refinement of the methodology before proceeding with additional larger studies.

12.4 Study endpoints

Partial nephrectomy

PRIMARY

- Detect the presence and extent of fluorescence of cT1 RCC in partial nephrectomy specimens at the margins of resection.

SECONDARY

- To assess the specificity of tumor fluorescence obtained using OTL38 with FR α + renal cell carcinoma cancer lesions detected via immunohistochemistry
- To assess pathologic agreement between fluorescence imaging using OTL28 and FR α by immunohistochemistry
- To assess the agreement between fluorescence imaging using OTL38 and visual/tactile assessments
- To assess inter-observer variations of tumor fluorescence images captured during surgery
- To assess physician rated usefulness of intra-operative fluorescence imaging- Likert scale questionnaire (**Appendix A**)
- To assess the safety of OTL38 (perioperative, 1-month)- Vital signs, hematology, chemistry, and adverse events (NCI-CTCAE v4.0)

Radical nephrectomy and lymph node dissection

PRIMARY

- To detect the presence and extent of fluorescence in regional lymph nodes and metastases in patients with RCC.

SECONDARY

- To assess the pattern of (lymph) nodal spread during radical nephrectomy
- To assess the degree of agreement of (lymph) nodal and primary tumor fluorescence during radical nephrectomy
- To assess the detection of RCC in primary tumor in situ during radical nephrectomy
- To assess the pathologic agreement of fluorescence and FR α by immunohistochemistry
- To assess the agreement between fluorescence imaging using OTL38 and visual/tactile assessments
- To assess inter-observer variations of tumor fluorescence images captured during surgery
- To assess surgeon opinion of usefulness of intra-operative fluorescence imaging-Likert scale questionnaire (**Appendix A**)
- To assess the safety (perioperative, 1-month) of OTL38-Vital signs, hematology, chemistry, and adverse events (NCI-CTCAE v4.0).

12.5 Participant characteristics

Demographics, medical history, and physical examination characteristics will be summarized using descriptive statistics.

12.6 Concomitant medications

Concomitant medications will be coded using the WHO Drug dictionary and will be summarized in tabular format.

12.7 Analysis of primary objective

The primary endpoint is to see if OTL38 and fluorescence imaging has sensitivity to detect RCC in the primary tumor (for partial nephrectomy) or in lymph nodes (for radical nephrectomy with lymph node dissection). Both sensitivity and the secondary endpoint of specificity will be assessed as follows: Final pathology and immunohistochemistry will serve as the gold standard with which gross observation and fluorescent imaging are compared for margin of resection, regional lymph nodes, and primary tumor. Pathology and immunohistochemistry results will be listed per patient. Times on and off for the imaging system will be listed per patient. Sensitivity, specificity, positive predictive value, and negative predictive value will be calculated for descriptive purposes although we understand the sample sizes are not large enough to estimate these values with a high level of accuracy at this stage. That would be accomplished in a future larger study. Sensitivity and specificity will be estimated using the method of Generalized Estimating Equations (GEE), which will take into consideration the correlated nature of multiple lesions removed from the same patient. Each patient will have all excised target lesions contributing to the data analysis (each type: O, x, ⊗, and P).

	Cancer +	Cancer-
Fluorescence+	True Positive (TP)	False Positive (FP)
Fluorescence-	False Negative (FN)	True Negative (TN)

Sensitivity (proportion of true positives) = $(TP/TP+FN) \times 100$

Specificity (proportion of true negatives) = $(TN/FP+TN) \times 100$

Sensitivity will be estimated using the GEE model for binomial distribution with fluorescence (-, +) as the fixed effect and patients as a random effect, and the 95% lower one-sided confidence interval for the true sensitivity will also be estimated. Specificity will be estimated using the GEE model for binomial distribution with fluorescence (-, +) as the fix effect and patients as a random effect, and the 95% lower one-sided confidence interval for the true specificity will also be estimated. Positive and negative predictive value will be estimated using similar methods.

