3.2 Advanced RCC

Between 1990 and 2006 the death rate decreased 21% on average for all malignancies in the US, but for kidney cancer it decreased by 6.9% (Jemal 2010). This placed kidney cancer 11th out of the 16 reported malignancies in the SEER database in terms of improving death rate. Despite the introduction of several new systemic therapies for advanced RCC, there are limited options that offer a reliable complete response. Cytoreductive nephrectomy continues to be the standard of

care, but the role for lymph node dissection is under investigation. We propose investigating the ability of real-time targeted imaging with folate tagged fluorescence to determine who should undergo lymph node dissection (LND) and the extent of that dissection.

Of those undergoing nephrectomy for localized disease, up to 18% will have recurrence or progression (Crispen 2008). Theoretically, many of these could benefit from a LND. However, as partial nephrectomy replaces radical nephrectomy for larger tumors, arguably fewer LNDs will be performed. Although previous studies have concluded that a LND can provide a durable progression free survival, the criteria for selection of patients who will most likely benefit from a LND remains a challenge (Delacroix 2011).

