6.2 Inclusion criteria for advanced RCC treated with radical nephrectomy

To be considered eligible to participate in this study, a patient must meet all the inclusion criteria listed below:

- ≥ 18 years of age.
- Have pathologic or suspected diagnosis of RCC with presence of cT1-4 renal mass and evidence of nodal or metastatic involvement by diagnostic CT assessment
- Scheduled for radical nephrectomy and lymph node dissection.
- Expected survival of at least 3 months.
- ECOG ≤ 2 .
- Negative serum or urine pregnancy test within 24 hours for females of child bearing age.
- Recovered from toxicity of any prior therapy to \geq grade 1
- Written informed consent available.

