 - Begin administration of study medication less than 2 hours prior to the skin incision on day of surgery in the preoperative area.
 - Record time of study medication administration
 - Record time of scheduled surgery (listed operating room time)
- AE assessment: including hypersensitivity reactions, which could include skin reactions, difficulty breathing, eye or nasal reactions, or gastrointestinal complaints, redness, tenderness, pain, or rash at the injection site or any clinically relevant abnormality (with exception of surgical scars) noted after the start of the study medication that was not present at screening.

8.3.2.2 Surgery:

The da Vinci[®] Fluorescence Imaging Vision System, SPY Elite Imaging System or Visionsense VSiii 3DHD system will be used to identify tumor lesions under normal/visible light and fluorescent light prior to surgical excision of lesions, and again after surgical excision of lesions to identify persistent lesions. The da Vinci system or Visionsense VSiii system will be used for all partial nephrectomies (robotic) and for robotic radical nephrectomies. The SPY Elite will be used for open radical nephrectomies. See **Appendix D** and **Appendix E** for more detailed information about the da Vinci and SPY camera/imaging systems. Information about the Visionsense VSiii system can be found at <http://www.visionsense.com/vsiii-system/>.

The Investigator will record the start and stop time for each exposure to fluorescence (pre-resection, post-initial resection, other [give reason]) in the eCRF. The total time of fluorescence will be calculated automatically.

Status	Time On Fluorescent Light	Time Off Fluorescent Light
Before surgical excision		
After initial surgical excision		
Other (explain reason)		

The number and location of suspect tumor lesions detected under **normal light and/or by palpation** will be recorded on the schematic (**Appendix B**) using an “O”. The number and location of suspect tumor lesions detected using **fluorescent light** will be recorded on the schematic using an “x” (for those lesions that were also identified under normal light and/or by palpation, the “x” will be superimposed on the “O” as “⊗”; and for those identified only under fluorescence, they will be recorded only by the “x”).

Light source	Notation
Visible light	O
Fluorescent	X
Both	⊗

For Partial Nephrectomies

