Surrounding perinephric fat will be removed as indicated for the renal mass. Then the renal mass will be visualized and photographed (video and still images) using visible light and fluorescent light. As described above, start and stop times of exposure to fluorescent light will be noted, and the number and location of fluorescent lesions related to the mass and surrounding renal parenchyma detected will be recorded on the schematic. Findings under visible light will also be recorded.

After the renal mass is removed, it will be processed by the operating surgeon and the frozen section pathology staff. The tumor margin will be inked and the tumor sectioned in 5mm thick cross-sectional slices. The tumor will then be returned to the operating room to be viewed and photographed with visible and fluorescent light. It will then be sent for pathologic processing as discussed in **Appendix B**.

For Radical Nephrectomies

The regional lymphadenectomy will be performed as per the standard of care for the patient’s renal mass. The renal mass will be visualized and photographed (video and still images) using visible and fluorescent light *through the surrounding perinephric fat*. The start and stop times of exposure to fluorescent light will be noted, and the number and location of fluorescent lesion/s related to the mass and surrounding renal parenchyma detected under fluorescent and visible light sources will be recorded on the schematic.

All identified nodal tissue from each marking (“O”, “X”, and “⊗”) will be excised, as determined by the Investigator, *under normal light*. Following the initial excision under normal light, the field will be illuminated with *fluorescent light* again to detect any remaining fluorescence-positive lesions. Any such lesions will be noted with a “P” on a schematic sheet (**Appendix C**) and excised as determined by the Investigator. A unique identifier will be assigned to each excised lesion, and the location for each lesion will be recorded on the schematic and in the eCRF. The reason for not excising any remaining lesion(s) will be noted. If no additional lesions are observed, this will be noted on the schematic and in the eCRF.

The nodal tissue will be processed by the operating surgeon and the frozen section pathology staff. The lymph nodal tissue will be marked with suture or clips to help with anatomic orientation of the specimen, and then sent for pathologic processing as discussed in the study pathology manual.

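### Arm 2 nodal sensitivity: the lesion types listed in 12.7 leave out excised cancerous nodes that neither method marked, so TP/(TP+FN) is too high if any such node exists

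*Combined protocol and SAP*

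**What the plan says.** All references are to the combined protocol and SAP.

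- **Target.** Section 12.7 makes the primary measure the sensitivity of fluorescence to detect RCC in the primary tumor for Arm 1, "or in lymph nodes (for radical nephrectomy with lymph node dissection") for Arm 2. Section 12.4 words the Arm 2 endpoint as regional nodes and metastases. Section 3.2 gives the intended use: "to determine who should undergo lymph node dissection (LND) and the extent of that dissection".
- **Data admitted.** Section 12.7: "Each patient will have all excised target lesions contributing to the data analysis (each type: O, x, ⊗, and P"). The term target lesion is not defined.
- **Marks (8.3.2.2).** O is a lesion suspected under normal light or by palpation. ⊗ is one found by both methods. For fluorescence alone, "for those identified only under fluorescence, they will be recorded only by the" x. After the first excision the field is lit "again to detect any remaining fluorescence-positive lesions", and these receive P.
- **Tissue removed in Arm 2 (8.3.2.2).** "The regional lymphadenectomy will be performed as per the standard of care". The nodal tissue goes to pathology.
- **Reference standard (12.7).** Final pathology and immunohistochemistry.
- **Use of the result (12.3).** If observed sensitivity is not at least 70% in each arm, refinement of the method will be considered before larger studies.

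**The concern.** Three of the four admitted types are fluorescence-positive by definition, so the fluorescence-negative row of the 12.7 table can be filled only by O-only lesions. Whether a fluorescence failure counts as a failure then depends on whether the surgeon had independently suspected that node.

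That does not fit the stated target. If imaging is meant to inform who has a dissection and how far it goes, a cancerous node that was in view and did not fluoresce is a miss, suspected or not. The misses left out are those that sight and touch also failed to find, which are the ones that matter most for that use.

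At stake is the Arm 2 primary measure and its comparison with 70%. The caveat in 12.7 about small samples covers imprecision. It does not cover a selection of the denominator, which a larger study would inherit if it reused the definition.

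**Working it through.** **1. The plan's own figures.** The only calculated design figure in 12.3 is the toxicity probability: 1 − 0.9^20 = 0.878, which reproduces the stated 88% but has no bearing here. The documents give no expected node counts and no power or precision figure for sensitivity. All counts below are therefore assumed.

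**2. Where each excised cancerous node goes.**

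| Mark | Fluorescence | Cell in the 12.7 table |
|---|---|---|
| x | + | true positive |
| ⊗ | + | true positive |
| P | + | true positive |
| O only | − | false negative |
| neither | − (if its area was viewed) | none |

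**3. Direction under the plan's formula.** Let u be the number of excised cancerous nodes from viewed areas that neither method marked. The plan computes TP/(TP+FN). Counting those nodes gives TP/(TP+FN+u), which is smaller whenever TP ≥ 1 and u ≥ 1. With TP = 0 and FN ≥ 1 both are 0%. If no cancerous node is O-only and TP ≥ 1, the plan's figure is 100% whatever u is.

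**4. Illustrative size.** Sensitivity after adding u omitted nodes:

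| Observed | u = 1 | u = 2 | u = 3 | First u below 70% |
|---|---|---|---|---|
| 7/10 = 70.0% | 7/11 = 63.6% | 7/12 = 58.3% | 7/13 = 53.8% | 1 |
| 8/10 = 80.0% | 8/11 = 72.7% | 8/12 = 66.7% | 8/13 = 61.5% | 2 |
| 9/10 = 90.0% | 9/11 = 81.8% | 9/12 = 75.0% | 9/13 = 69.2% | 3 |
| 16/20 = 80.0% | 16/21 = 76.2% | 16/22 = 72.7% | 16/23 = 69.6% | 3 |

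The same effect seen from the other side: suppose 12 of 20 cancerous nodes fluoresce (60%). If 3 of the 8 misses are unmarked, the plan reports 12/17 = 70.6% and passes the mark. If 2 are unmarked, it reports 12/18 = 66.7% and does not. Exact one-sided 95% lower bounds, ignoring clustering, are 39% for 12/20 and 48% for 12/17. The bound is weak either way, so the effect that matters is on the point estimate.

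**5. Direction under GEE.** Section 12.7 plans GEE but names no working correlation. The check used intercept-only binomial GEE on simulated cancerous nodes (10 patients, 1 to 4 nodes each, both assumed) and added one false negative to each data set. The estimate fell in 397 of 397 data sets with independence correlation and in 384 of 397 with exchangeable correlation. In the other 13 it did not fall.

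**The case against.** **The list may not be closed.** Target lesion is undefined, and the reference-standard sentence in 12.7 names regional lymph nodes without limiting them to marked ones. A lenient reader could count every node. This stands as a reason to clarify, but it does not rescue the text: the parenthesis lists the types, and none covers an unmarked node.

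**No such node may occur.** O includes palpation, and 6.2 requires "evidence of nodal or metastatic involvement by diagnostic CT assessment". Every cancerous node could be marked, and then nothing changes. This stands. It makes the bias conditional, not impossible: CT evidence may be metastatic rather than nodal, and the dissection is not confined to suspicious nodes.

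**Other readings exist.** The Appendix A ex-vivo form images and grades enlarged nodes and metastases after removal, so some unmarked nodes will have a fluorescence reading. Pathology is also listed per patient, so an unmarked positive node could be seen. Both narrow the data gap, but 12.7 does not bring either into the table. The study pathology manual, the eCRF and the Appendix C drawing cannot be seen here and may help match nodes to marks.

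**The stakes are low.** Section 12.7 calls the estimates descriptive, and missing 70% triggers only consideration of refinement. This stands and limits the consequence.

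**A reader might go further** and infer that every planned estimate can only be biased upward. The documents support that for the stated ratio, not for a GEE whose correlation is unspecified. A reader might also infer that specificity and NPV are wrong. Leaving out unmarked benign nodes makes them conditional on a lesion having been marked. That is a different population needing a label, not clearly an error.

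**Conclusion.** The point holds in conditional form. Under the types listed in 12.7, only a lesion already suspected by sight or palpation can be a false negative. An excised cancerous node from a viewed field that neither method marked is not counted. If at least one exists and TP ≥ 1, TP/(TP+FN) overstates Arm 2 sensitivity; a GEE estimate will usually, not always, shift the same way.

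The size cannot be derived from the documents. With about 10 cancerous nodes, an assumed figure, one or two omitted nodes are enough to take an observed 70% to 80% below the 70% mark.

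The conclusion rests on three readings: the parenthesis in 12.7 is an inclusion rule, the in-situ mark is the test result, and the dissection can remove unmarked nodes. The documents do not show that inflation will occur, nor that a wrong go/no-go decision would follow. It should be fixed because it affects the Arm 2 primary measure and the remedy is small.

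**What to change.** For Arm 2, amend 12.7 along these lines:

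- Every excised node or metastasis with a reference-standard result under 12.7 (final pathology and immunohistochemistry, as the plan defines it) contributes to sensitivity.
- It is fluorescence-positive if marked x, ⊗ or P. It is fluorescence-negative if its area was viewed under fluorescent light and it was not so marked.
- Specimens from areas not viewed are listed as not evaluable.
- The in-situ mark is the test result. Ex-vivo grades of removed enlarged nodes and metastases (Appendix A) are listed as supplementary.
- The unit is fixed before analysis: the node, or the labelled specimen or nodal region if nodes cannot be matched to marks.
- Sensitivity among marked lesions is reported as supplementary. Specificity and NPV are each labelled with the population used.

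The GEE working correlation should be named at the same time.

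**Cost.** SAP wording, a category for neither method and a record of areas viewed on the schematic and eCRF, and some extra specimen labelling. The plan already provides part of this: "The lymph nodal tissue will be marked with suture or clips to help with anatomic orientation of the specimen". A regional unit is coarser, since a region with one fluorescing and one missed cancerous node counts as detected. Reported sensitivity may be lower. The surgery itself is unaffected.

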Outcomes:	
Partial nephrectomy
 
PRIMARY
 
 Assess the presence and extent of fluorescence of cT1 RCC during partial nephrectomy 
SECONDARY
 
 Pathologic agreement of fluorescence and FR α by immunohistochemistry Agreement between visual and fluorescent images Inter-observer agreement of laparoscopic fluorescent images (for blinded surgeons) Surgeon opinion of usefulness of intra-operative fluorescence imaging-Likert scale questionnaire (Appendix A) Safety (perioperative, 10 days, 1-month)- Vital signs, hematology, chemistry, and adverse events (NCI-CTCAE v4.0)
	
Radical nephrectomy and lymph node dissection
 
PRIMARY
 
 Assess the presence and extent of fluorescence in regional lymph nodes or metastasis in patients with RCC 
SECONDARY
 
 Pattern of nodal spread Agreement of nodal and primary tumor fluorescence Pathologic agreement of fluorescence and FR α by immunohistochemistry Detection of RCC in primary tumor in situ Agreement between visual and fluorescent images. Inter-observer agreement of in-situ fluorescent images (for blinded surgeons) Surgeon opinion of usefulness of intra-operative fluorescence imaging- Likert scale questionnaire (Appendix A) Safety (perioperative, 10 days, 1-month)-Vital signs, hematology, chemistry, and adverse events (NCI-CTCAE v4.0)

LIST OF ABBREVIATIONS AND TERMS

[figure not shown]
Abbreviation/Term	Definition
ADE	Adverse device effect
AE	Adverse event
BMP	Basic metabolic panel
CBC	Complete blood count
CMP	Comprehensive metabolic panel
CRF	Case report form
CT	Computed tomography
CTMS	Clinical Trial Management System
CTO	Clinical Trials Office
CTSI	Indiana Clinical and Translational Sciences Institute
DSMC	Data Safety Monitoring System
ECOG	Eastern Cooperative Oncology Group
FDA	Federal Drug Administration
FR	Folate receptor protein
FITC	Fluorescein isothiocyanate
GFR	Glomerular filtration rate
IDS	Investigational Drug Service
IHC	Immunohistochemistry
IND	Investigational new drug
IUH	Indiana University Hospital
IUSCC	Indiana University Simon Cancer Center
LND	Lymph node dissection
REDCap	Research Electronic Data Capture
RCC	Renal cell carcinoma
SAE	Serious adverse event
SEER	Surveillance epidemiology and end results

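### In the radical-nephrectomy arm, Section 12.7 pools lesions found on a post-excision fluorescent look (P) with first-look lesions, which raises fluorescence sensitivity and tilts the comparison with gross observation

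*Combined protocol and SAP*

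**What the plan says.** **Marks.** Section 8.3.2.2 defines O for a suspect lesion found by sight or touch, x for one found under fluorescence, and ⊗ for both. On the O mark: "The number and location of suspect tumor lesions detected under normal light and/or by palpation will be recorded on the schematic".

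**Second look.** Under the radical-nephrectomy heading of 8.3.2.2, nodal tissue marked O, x or ⊗ is excised under normal light. The field is then lit with fluorescent light "again to detect any remaining fluorescence-positive lesions. Any such lesions will be noted with a “P” on a schematic sheet". These lesions are excised as the investigator decides, and each excised lesion receives its own identifier. No rule links a P lesion to an earlier mark.

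**General imaging paragraph.** Earlier in 8.3.2.2, for all surgeries, the camera systems are to identify lesions "under normal/visible light and fluorescent light prior to surgical excision of lesions, and again after surgical excision of lesions to identify persistent lesions".

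**Analysis.** Section 12.7 builds one table of fluorescence against cancer and estimates sensitivity and specificity by GEE. On which lesions count: "Each patient will have all excised target lesions contributing to the data analysis (each type: O, x, ⊗, and P"). It makes final pathology and immunohistochemistry "the gold standard with which gross observation and fluorescent imaging are compared". Section 12.8 adds kappa statistics and a paired t-test on the number of lesions found by each method.

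**Threshold.** Section 12.3 says that an observed sensitivity below 70% in each arm would lead the team to consider refining the method before larger studies.

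**The concern.** The first look (x, ⊗) asks whether fluorescence finds disease in place. The second look (P) asks whether anything fluorescent remains in an opened field. Section 12.7 puts both into one sensitivity without saying which reading sets a lesion's fluorescence status.

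P lesions are also selected on the test result. A lesion enters this category only because it fluoresces, so the category can add true positives or false positives, but never false negatives. A cancer that fluorescence did not mark before excision is then scored as a detection. No post-excision mark exists for sight or palpation, so the same lesion is a miss for gross observation.

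Two results are at stake: the radical-arm sensitivity that is held against 70%, which is the only efficacy criterion the plan states, and any lesion-level contrast between fluorescence and gross observation. A P lesion that is the remnant of an x or ⊗ lesion could also be counted twice.

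**Working it through.** **The plan's own figures.** The only computed figure in Section 12.3 is the 88% chance of at least one toxicity event: 1 − 0.9^20 = 0.878. It reproduces but does not bear on this point. The 70% line has no calculation behind it.

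**How each mark enters the tables** (from 8.3.2.2 and 12.7):

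| Mark | Fluorescence | Sight/palpation |
|---|---|---|
| O | negative | positive |
| x | positive | negative |
| ⊗ | positive | positive |
| P | positive by definition | no mark defined |

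Of the four types, only O lesions can be false negatives for fluorescence.

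**Formulas.** Let n be the first-look cancers that were excised, a the number of these that were fluorescent on the first look, and c the number of new cancerous P lesions.
- P as true positive (plain reading of 12.7): (a + c)/(n + c)
- P excluded: a/n
- P scored by the first look, i.e. missed: a/(n + c)

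For c > 0 and a between 0 and n, the first always exceeds the second, and the second always exceeds the third.

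**Range.** The documents give no lesion counts, so a, n and c are assumptions.

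| a/n | c | P as true positive | P excluded | P as miss |
|---|---|---|---|---|
| 12/18 | 2 | 14/20 = 70.0% | 66.7% | 12/20 = 60.0% |
| 6/10 | 4 | 10/14 = 71.4% | 60.0% | 6/14 = 42.9% |
| 13/20 | 4 | 17/24 = 70.8% | 65.0% | 13/24 = 54.2% |
| 12/20 | 7 | 19/27 = 70.4% | 60.0% | 12/27 = 44.4% |

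In each row c is the smallest number that reaches 70% when P counts as a true positive.

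**Chance of observing at least 70%.** Assume a true first-look sensitivity of 60% and independent lesions (a simplification, since lesions cluster within patients).
- n = 18, c = 2. P excluded needs 13 of 18: 20.9%. P as true positive needs 12 of 18: 37.4%. P as miss needs 14 of 18: 9.4%.
- n = 10, c = 4. P excluded needs 7 of 10: 38.2%. P as true positive needs 6 of 10: 63.3%. P as miss needs 10 of 10: 0.6%.
- n = 10 or n = 20, c = 1 or 2. Counting P as true positive gives the same chance as excluding it (38.2% and 25.0%), because of rounding to whole lesions.

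**Comparison with gross observation.** Let both methods find 7 of 10 cancers on the first look, with c = 2. Fluorescence becomes 9/12 = 75.0% and gross observation 7/12 = 58.3%. A tie turns into a gap of 16.7 points.

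**Other direction.** Cancer-negative P lesions are false positives. With 8 true negatives among 10 and two such lesions added, specificity falls from 80% to 8/12 = 66.7%.

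**The case against.** **Sensitivity over the whole procedure is a legitimate target.** Checking for residual tumor after resection is a stated use of the imaging. This stands: choosing the pre-excision look is partly a choice of estimand. It does not remove the need for 12.7 to say which look counts, or to keep the two apart.

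**The estimates are descriptive and the trial is a pilot.** This limits the stakes. The caveat in 12.7 concerns imprecision from small samples, however, and not a scoring rule that moves sensitivity in one direction.

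**A reader might infer that sight and palpation get no second look at all.** The documents do not support that. The general paragraph of 8.3.2.2 can be read as both lights before and after excision, and Appendix A has blinded surgeons mark white-light photographs of the fossa after removal, for inter-observer agreement. What can be said is that no post-excision sight or palpation finding has a mark or is scored in the lesion analysis.

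**A reader might infer that P lesions always favour fluorescence.** They do so only for sensitivity. Cancer-negative ones lower specificity and positive predictive value.

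**A reader might extend the point to both arms.** P is defined only for radical nephrectomy. For the partial arm, the synopsis has "Assess the presence and extent of fluorescence of cT1 RCC during partial nephrectomy" while 12.4 has "Detect the presence and extent of fluorescence of cT1 RCC in partial nephrectomy specimens". That leaves open whether an in-situ or a back-table reading counts, which is a separate question and does not show the P mechanism there.

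**The comparison with gross observation is not fully specified.** Section 12.7 gives no formula for gross-observation sensitivity, and 12.8 does not say whether P enters the kappa or the t-test. So the tilt applies to any such comparison that includes P. Double counting is likewise only possible, since recorded locations might allow remnants to be linked.

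**Conclusion.** The point holds for the radical-nephrectomy arm. Followed as written, 12.7 gives fluorescence credit for lesions selected because they fluoresced on a later look. This raises sensitivity, and it tilts any lesion-level contrast with gross observation that includes P.

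The size cannot be known from the documents. Under the assumed 12 of 18 plus 2, sensitivity runs from 60% to 70% by scoring rule alone. Crossing the 70% line is possible but not assured, and from 12/20 it would take seven cancerous P lesions. Results also depend on what P is compared with: with 12 of 17 on the first look and 3 P lesions, counting P gives 15/20 = 75%, but leaving P out gives 12/17 = 70.6%, which still meets the line. Only scoring P as misses (12/20 = 60%) falls below it.

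A reader might treat 70% as a go/no-go rule. Section 12.3 commits the team only to considering refinement, and no test is attached.

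**What to change.** 1. In 12.7, define Fluorescence+ and Fluorescence- for the 70% line by the pre-excision in-situ reading (x, ⊗).
2. Report sensitivity including post-excision P lesions on a separate line, showing P as true positive, excluded, and as first-look miss. Show specificity and positive predictive value with and without P.
3. Link a P lesion that is the remnant of an already marked lesion to that lesion's identifier, and do not count it again.
4. Leave P out of the comparisons with gross observation in 12.7 and 12.8, unless a matching post-excision normal-light or palpation finding is recorded before the fluorescent light goes back on.
5. Reconcile the general paragraph of 8.3.2.2 with its radical-nephrectomy paragraph on which light is used after excision.

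The cost is analysis-plan wording and one link field in the eCRF, plus one extra mark if the matching look is recorded. Look and linkage need recording at surgery, since they may not be recoverable later. The downside is that the headline sensitivity may be lower.
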